3.2.5 Vital Sign Measurements

Vital sign assessments will include measurements of sitting blood pressure (mm Hg), heart rate (beats per minute), respiration rate (breaths per minute), pulse oximetry, and oral

temperature (Celsius). Abnormal results are to be repeated after 5 minutes of rest. See [Table 5](#) for timing window allowances with respect to measurement collection.

Abnormalities in vital sign measurements will be graded in severity per the National Cancer Institute Common Terminology Criteria for Adverse Events (NCI CTCAE) scale Version 4.03.

3.2.6 12-Lead Electrocardiogram (ECG)

On dose administration days, digital 12-lead ECG measurements will be obtained at 5 minutes after the completion of the infusion. When ECGs are to be collected at the same time point as a blood collection, ECGs should be collected first. ECGs are to be performed in triplicate at least 1 to 2 minutes apart (Cohort 1) or approximately 1 minute apart (Cohort 2). See [Table 5](#) for timing window allowances with respect to performing ECG.

The following ECG parameters will be collected: PR interval, RR interval, QRS interval, and QT interval. The ECG findings will be evaluated by a qualified physician for the presence of abnormalities (qualitative assessment). The physician will assess each ECG as normal, abnormal/not clinically significant, or abnormal/clinically significant.

Normal corrected QT interval using Fridericia's formula QTcF is ≤ 450 msec.

Abnormalities in the ECG that appear following therapy or that result in clinical signs and symptoms are considered clinically significant for the purposes of this study and will be recorded on the AE eCRF.

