4.7.2 Clinical Laboratory Tests

Laboratory results, percentage change and absolute change from baseline will be summarized by cohort, visit and time point using descriptive statistics. Incidence of laboratory abnormalities and laboratory NCI CTCAE (Version 4.03) will be summarized. Shift tables of CTCAE Grade for chemistry parameters (Normal, Grade 1, Grade 2, Grade 3, Grade 4, Grade 3/4, Total, Missing) from baseline to each post-baseline time point showing number and percentage of subjects with movement between categories will be presented. The worst on-study grade after the first study drug administration will also be summarized.

Baseline is defined as the Day 0 (pre-dose) measurement. If the baseline measurement is missing, the last measurement prior to the first study drug administration will be used.

Results, normal limits of the local laboratory, and abnormality flags will be listed.

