4.7.3 Physical Examination, Vital Signs, and Electrocardiogram Findings

The number and percentage of subjects with normal, abnormal and clinically significant, abnormal but not clinically significant physical exam findings will be summarized by visit and dose.

Vital sign measurements and change from baseline will be summarized at each scheduled time point by cohort using descriptive statistics. Baseline is defined as the Day 0 (pre-dose) measurement. If the baseline measurement is missing, the last measurement prior to the first study drug administration will be used.

The arithmetic mean of parameters from triplicate ECGs will be calculated first for each participant at each planned time point. Then summary statistics for ECG test parameters (mean of triplicate) and change from baseline to each post-dose time point will be calculated. Shift tables for ECG test result category changes (normal, abnormal not clinically significant, abnormal clinically significant) from pre-dose to each post-dose time point showing number and percentage of subjects with changes between categories will be presented by cohort.

The number and percentage of subjects experiencing potential QTcF prolongation (QTcF > 450, >480 and >500 msec, and change from baseline in QTcF >30 and >60 msec) will be summarized at each time point by cohort.

Actual sampling times that are outside the scheduled sampling times window described in [Table 5](#) will be excluded from summary statistics.

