4.8 Analysis of Secondary Endpoints

4.8.1 Pharmacokinetic Analysis

PK results for SYNT001 will be summarized by cohort, visit and time point.

Descriptive statistics will be provided for the PK parameters including mean, SD, CV, median, minimum, and maximum.

For calculation of mean concentrations and generation of mean concentration-time profiles, all below the limit of quantification (BLQ) values will be set to zero except when an individual BLQ falls between 2 quantifiable values, in which case it will be omitted.

If there are values above the BLQ, but too sparse to allow full analysis, descriptive statistics will be performed on available values.

PK concentrations will be summarized descriptively at each nominal time point by cohort using n, mean, SD, percent coefficient of variation (CV%), standard error, median, minimum, maximum, geometric mean, geometric CV%.

Mean concentrations (\pm SD) of SYNT001 will be plotted on a linear and semi-logarithmic scale against nominal time points, by cohort. Individual concentration for each subject will be plotted using original scale and semi-log scale.

Study drug serum concentration data will be used to calculate the following PK parameters, if feasible:

Parameters	Description
C_{\max}	Maximum observed plasma concentration observed directly from data at Day 0 and Day 28
T_{\max}	Time to reach maximum observed concentration directly from data at Day 0 and Day 28
λ_z	Apparent first-order terminal elimination rate constant calculated by linear regression of the terminal linear portion of the log concentration vs. time curve at Day 0 and Day 28
$t_{1/2}$	Terminal elimination half-life, calculated as $\ln(2)/\lambda_z$ at Day 0 and Day 28
AUC_{0-24}	AUC from time zero to 24 hours post-dose administration at Day 0 and Day 28
AUC_{∞}	AUC from time zero to infinity time (as $AUC_{0-t} + C_{\text{last}}/\lambda_z$, where C_{last} is the last quantifiable concentration) at Day 0 and Day 28

Actual sampling time will be used for PK calculations. Actual sampling times that are outside the scheduled sampling times window described in [Table 5](#) will be excluded from summary statistics of average PK SYNT001 serum concentrations but will still be used in the calculation of PK parameters.

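### SAP 4.7.3 removes out-of-window dosing-visit vital signs from the only planned vital-sign summary, and no worst-value table keeps them

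*SAP*

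**What the plan says.** SAP 2.1.1 and Protocol 3 both name vital signs in the primary safety endpoint. For their analysis, SAP 4.7.3 plans one summary: "Vital sign measurements and change from baseline will be summarized at each scheduled time point by cohort using descriptive statistics". SAP 4.1 defines descriptive statistics as n, mean, SD, median, quartiles, minimum and maximum.

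The last sentence of 4.7.3 then states: "Actual sampling times that are outside the scheduled sampling times window described in [Table 5](#) will be excluded from summary statistics". Table 5 in SAP Appendix A covers dosing visits. Its vital-sign windows are 240 minutes before the infusion up to its start; ±5 minutes at 15, 30 and 45 minutes after the start; ±10 minutes at completion; and ±10 minutes at 30, 60 and 120 minutes after the end.

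On grading, SAP 3.2.5 says: "Abnormalities in vital sign measurements will be graded in severity per the National Cancer Institute Common Terminology Criteria for Adverse Events". No table of those grades appears in SAP 4.7.3.

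For ECGs, 4.7.3 plans three outputs: continuous summaries ("Then summary statistics for ECG test parameters (mean of triplicate) and change from baseline to each post-dose time point will be calculated"), shift tables, and threshold counts ("The number and percentage of subjects experiencing potential QTcF prolongation").

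Protocol 11.5 plans the same by-time-point vital-sign summary without any window exclusion.

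**The concern.** Dropping mistimed readings from a nominal-time table is a sound way to keep that table interpretable. The difficulty is that for vital signs no other table catches what is dropped.

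In a descriptive study of at most 20 subjects, single extreme values show up in a vital-sign table mainly through the minimum and maximum. An out-of-window extreme would be missing from both. The n at that time point would fall, but the table would not separate an excluded reading from a missing one. Someone who relies on the tables for this component of the primary endpoint could not tell that a value had been measured and set aside.

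Elsewhere the SAP does provide a second route. For laboratory data, 4.7.2 says: "The worst on-study grade after the first study drug administration will also be summarized". For PK samples, 4.8.1 says that out-of-window times "will be excluded from summary statistics of average PK SYNT001 serum concentrations but will still be used in the calculation of PK parameters".

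**Working it through.** **1. Does the rule reach vital signs?** Section 4.7.3 deals only with physical examination, vital signs and ECG. Of these, Table 5 gives windows for vital signs and ECG. The closing sentence names no exception. Read with SAP 4.1, which separates continuous data (descriptive statistics) from categorical data (frequencies and percentages), it applies to the continuous by-time-point summaries of both.

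**2. Does any other planned table hold the value?**

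| Place | What it summarizes | Keeps an out-of-window vital sign? |
|---|---|---|
| SAP 4.7.3, vital signs | Values and change by time point | No |
| SAP 4.7.2 | Laboratory results and worst laboratory grade | Not applicable |
| SAP 4.7.1 | TEAEs by worst grade; infusion-reaction AEs separately | Only if reported as an AE |
| SAP 4 | Listings of all captured data | Yes, but a listing is not a summary |

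**3. How many readings fall under the rule?** The schedules in SAP Appendix A (Tables 2 to 4) give 8 vital-sign time points per dosing visit: 1 before the infusion and 7 after it starts (15, 30 and 45 minutes; completion; 30, 60 and 120 minutes after the end). SAP 3.1 gives the doses and the maximum subjects.

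Sets after infusion start = 7 × doses × subjects:

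- Cohort 1: 7 × 5 × 8 = 280
- Cohort 2, every other week: 7 × (3 + 5) × 12 = 672
- Cohort 2, weekly alternative: 7 × (3 + 10) × 12 = 1092

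Pre-infusion readings are left out of the count. Their window is 240 minutes wide, and they are due immediately before the infusion. Table 5 lists pulse oximetry for Cohort 1 only, so the Cohort 2 sets are blood pressure, pulse, respiratory rate and temperature.

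**4. What would be dropped?** The documents give no out-of-window rate, so this step is illustration only. Assume a rate q per reading set, independent between sets. Expected sets dropped = q × sets. The chance that a given time point loses at least one subject is 1 − (1 − q)^n, with n = 8 or 12.

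| Assumed q | Cohort 1 dropped | Cohort 2 every other week | Cohort 2 weekly | Chance, n = 8 | Chance, n = 12 |
|---|---|---|---|---|---|
| 2% | 5.6 | 13.4 | 21.8 | 15% | 22% |
| 5% | 14.0 | 33.6 | 54.6 | 34% | 46% |
| 10% | 28.0 | 67.2 | 109.2 | 57% | 72% |

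These figures count readings removed. They do not say how many would be extreme, so they do not estimate bias.

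**The case against.** **The rule might not cover vital signs.** The vital-sign sentence speaks of descriptive statistics, the exclusion of summary statistics, and the latter phrase otherwise appears in 4.7.3 only for ECG parameters. That leaves some room for doubt. But Table 5 lists vital signs, the sentence has no carve-out, and SAP 4.1 treats all continuous data alike. If vital signs were not meant to be covered, the text should say so.

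**The contrasts with PK and laboratory data are not inconsistencies.** This stands. PK concentration summaries by time point exclude out-of-window samples too; those samples survive only in parameters computed from actual times. Table 5 sets no window for safety laboratory tests. The two sections show that the SAP knows how to provide a second route, not that it contradicts itself.

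**There are other safety nets.** This also stands in part. All data are listed, which is workable for 20 subjects. Protocol 10.2 counts a worsened sign as an AE, so important abnormalities should reach the TEAE tables. SAP 1 permits supplementary analyses. These reduce the harm, but none puts the value in a planned vital-sign table, and the AE route depends on a report being made.

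**Repeat readings.** SAP 3.2.5 says: "Abnormal results are to be repeated after 5 minutes of rest". With a ±5-minute window, a first reading after the nominal minute pushes its repeat out of window. A reader might infer that the rule systematically discards repeats. The documents do not support that. They do not say whether the first or the repeat reading represents the time point, so a repeat might be absent from the table without this sentence, and the in-window first reading stays.

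**Conclusion.** The point holds as a minor gap in the safety summaries. An out-of-window vital-sign extreme at a dosing visit appears in no planned vital-sign table. At full enrollment, at most 280 post-start reading sets in Cohort 1 and 672 or 1092 in Cohort 2 fall under the rule. How many would be excluded, and in which direction that would move the summaries, cannot be determined from the documents.

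Two stronger readings should be resisted. A reader might infer that late ECGs are dropped from the QTcF counts and shift tables. The text does not say so: 4.7.3 uses the term *summary statistics* for the ECG parameter means, and SAP 4.1 handles categorical outputs separately. The only fault is that the SAP leaves this unsaid. A reader might also infer that loss is concentrated in subjects having infusion reactions, because Protocol 9.6.2 allows an infusion to be slowed or interrupted. The Table 5 windows are tied to the start and completion of the infusion, so a longer infusion does not by itself put a scheduled reading out of window. The link is possible but not shown.

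The conclusion assumes that the closing sentence applies to vital signs and that the stand-alone programming specifications (SAP 6) do not add a worst-value table.

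**What to change.** In SAP 4.7.3:

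1. Limit the window exclusion to the by-time-point continuous descriptive statistics.
2. Add one worst post-dose vital-sign summary by cohort, using every post-dose reading, with out-of-window readings and repeats included. Define worst in each direction for each parameter, or by the CTCAE grade already assigned under SAP 3.2.5.
3. Report the number of readings excluded, by cohort and time point, so that excluded and missing readings can be told apart.
4. As a clarification, state that QTcF threshold counts and ECG shift tables are not subject to the exclusion.

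The cost is a few sentences of SAP text, one extra derivation with its table, and a count of exclusions. No new data are needed. The worst-value summary will mix readings taken at somewhat different times after dosing, which is acceptable because it is not read as a time profile.

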4.8 Analysis of Secondary Endpoints

4.8.1 Pharmacokinetic Analysis

PK results for SYNT001 will be summarized by cohort, visit and time point.

Descriptive statistics will be provided for the PK parameters including mean, SD, CV, median, minimum, and maximum.

For calculation of mean concentrations and generation of mean concentration-time profiles, all below the limit of quantification (BLQ) values will be set to zero except when an individual BLQ falls between 2 quantifiable values, in which case it will be omitted.

If there are values above the BLQ, but too sparse to allow full analysis, descriptive statistics will be performed on available values.

PK concentrations will be summarized descriptively at each nominal time point by cohort using n, mean, SD, percent coefficient of variation (CV%), standard error, median, minimum, maximum, geometric mean, geometric CV%.

Mean concentrations (\pm SD) of SYNT001 will be plotted on a linear and semi-logarithmic scale against nominal time points, by cohort. Individual concentration for each subject will be plotted using original scale and semi-log scale.

Study drug serum concentration data will be used to calculate the following PK parameters, if feasible:

Parameters	Description
C_{\max}	Maximum observed plasma concentration observed directly from data at Day 0 and Day 28
T_{\max}	Time to reach maximum observed concentration directly from data at Day 0 and Day 28
λ_z	Apparent first-order terminal elimination rate constant calculated by linear regression of the terminal linear portion of the log concentration vs. time curve at Day 0 and Day 28
$t_{1/2}$	Terminal elimination half-life, calculated as $\ln(2)/\lambda_z$ at Day 0 and Day 28
AUC_{0-24}	AUC from time zero to 24 hours post-dose administration at Day 0 and Day 28
AUC_{∞}	AUC from time zero to infinity time (as $AUC_{0-t} + C_{\text{last}}/\lambda_z$, where C_{last} is the last quantifiable concentration) at Day 0 and Day 28

Actual sampling time will be used for PK calculations. Actual sampling times that are outside the scheduled sampling times window described in [Table 5](#) will be excluded from summary statistics of average PK SYNT001 serum concentrations but will still be used in the calculation of PK parameters.

PK parameters will be determined using non-compartmental method. The Linear Up Log Down method will be used in the computation of AUCs. The PK parameters λ_z and $t_{1/2}$ will not be presented for subjects who do not exhibit a terminal elimination phase in their concentration-time profiles.

The constant λ_z will not be assigned if one of the following happens:

1. T_{\max} is or is equal to one of the 3 last data points,
2. The adjusted regression coefficient is less than 0.8,
3. The percent of AUC_{∞} extrapolated exceeds 20%,
4. The estimated elimination rate indicates a positive slope, or
5. The terminal elimination phase is not linear (as appears in a semi-logarithmic scale) based on visual inspection.

In cases where the constant λ_z is not assigned, the values of associated parameters (e.g., $t_{1/2}$ and AUC_{∞}) will not be calculated.

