- h. Serology: Testing at Day 56 will not be done for any subject whose baseline titer is below the level of detection. If the Day 56 results are greater than 30% below the baseline value, or if the subject falls below the level of detection, the subject will be re-tested at Day 84; if still below the baseline value (or level of detection), the subject will be re-tested at Day 112. Any subject whose baseline value for tetanus or VZV was above the detectable level at baseline and is not within 30% of the baseline value or is below the detectable level by Day 112, will be referred to their primary care physician for further management. See Protocol Section 6.7.3 for additional information.
- i. PK: Starting on Days 0 and 28, serum samples will be collected just prior to the start of study drug infusion (pre-dose), and at 5 minutes and 2, 4, 6, 24, and 48 hours after the end-of-study drug infusion. Additional samples will be collected on Days 5 and 33. See Protocol Section 6.7.4 for additional information.
- j. Immunogenicity: Blood samples will be collected pre-dose when collected on dosing days. Samples will be collected on Days 0, 14, 28, 56, 84 and 112. See Protocol Section 6.7.6 for additional information.
- k. Prior to study drug infusion, SYNT001 drug product is to be diluted in dextrose 5% in water to a total volume of 250 mL and administered intravenously over 1 hour ±15 minutes using a 0.2-micron, inline filter. See Protocol Section 9 for additional information.
- l. Immunoglobulins (IgG, IgA, IgM) and IgG subtypes (IgG1-4): Collected for measurements of IgG, IgG subtypes (IgG1-4), IgA, IgM at every visit. On Days 0, 7, 14, 21, and 28, samples are collected prior to infusion of study drug.
- m. Subjects will return to the clinic on Days 84 and 112 for follow-up visits. Subjects whose total IgG is not within 30% of their Day 0 baseline value and not above 500 mg/dL at the Day 112 visit will be referred for further management.
- n. Additional PD samples to be collected for measurements of biomarkers, including D-dimer; antiphospholipid antibodies (lupus anticoagulant, anti-cardiolipin, and anti-beta-2-GP1 antibodies); antinuclear antibody titer; anti-double-stranded DNA antibody titer; complement component 3. See Protocol Section 6.7.5 for complete information.
- o. Buccal samples to be collected and stored.
- p. Immunophenotyping by flow cytometry for measurement of CD3⁺CD4⁺ T, CD3⁺CD8⁺ T, monocytes, natural killer (NK) cells, and B cells.

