- b. Vital sign measurements (sitting blood pressure, heart rate, respiratory rate, and oral temperature) to be obtained after 5 minutes of seated rest. Any abnormal measurements are to be repeated after 5 minutes of rest. Vital sign measurements will be taken on all study visits. On dosing days, vital sign measurements will be collected immediately prior to the infusion; 15, 30, and 45 minutes after the start of the infusion; at completion of the infusion; and 30 minutes, 1 hour and 2 hours following completion of the infusion.
- c. Pulse oximetry: On dosing day, pulse oximetry to be measured immediately prior to the infusion; 15, 30, and 45 minutes after the start of the infusion; at completion of the infusion; and 30 minutes, 1 hour, and 2 hours following completion of the infusion.
- d. Clinical safety labs: hematology, clinical chemistry, and urinalysis. See Protocol Section 6.7 for a complete list. Full clinical safety lab draws will be collected at screening and at all study visits prior to infusion if applicable. PD markers (albumin levels, hematocrit, hemoglobin, platelet count, reticulocyte count, lactate dehydrogenase, and total and indirect bilirubin) will be derived from the clinical safety laboratory results.
- e. Pregnancy test (women of childbearing potential only): To be performed at time of screening and prior to dose on dosing days if applicable. Urine or serum test is acceptable; however, positive urine tests must be confirmed with serum testing.
- f. Digital 12-lead ECG to be obtained after 5 minutes of rest in the supine position and in triplicate approximately 1 minute apart. See Protocol Section 6.6 for additional information. On days of treatment, to be obtained 5 minutes after the completion of infusion.
- g. Serology: Any subject whose baseline value for tetanus or VZV was above the protective level at baseline and is not within 30% of the baseline value or is below the protective level by End of Follow-up, will be referred to their primary care physician for further management. See Protocol Section 6.7.3 for additional information.
- h. PK: Starting on dosing days, serum samples will be collected just prior to the start of study drug infusion (pre-dose) and at 5 minutes, 1 and 2 hours after the end of study drug infusion. See Protocol Section 6.7.4 for additional information.
- i. Immunogenicity: Samples will be collected pre-dose when collected on dosing days. See Protocol Section 6.7.6 for additional information.

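### SAP 4.8.1 does not confine its BLQ omission rule to one dose, so read literally it drops BLQ troughs from the mean; its Day 28 AUC to infinity in Cohort 1 includes carry-over but shares the Day 0 definition

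*SAP*

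**What the plan says.** Under SAP 4.8.1, a BLQ result counts as zero in mean concentrations and mean profiles. The one exception is worded as follows: "except when an individual BLQ falls between 2 quantifiable values, in which case it will be omitted". Protocol 11.4 has the same rule. Neither says that the two neighbouring values must follow the same dose.

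The same SAP section summarizes concentrations at each nominal time point with, among others, "standard error, median, minimum, maximum, geometric mean, geometric CV" (in percent). It has no rule for zeros in those statistics.

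The parameter table in SAP 4.8.1 defines one quantity, "AUC from time zero to infinity time", for both Day 0 and Day 28. It is the AUC to the last quantifiable sample plus that concentration divided by λz. The plan has no AUC over the dosing interval and no correction for the Day 28 pre-dose level. λz, and with it half-life and AUC to infinity, is withheld when the percentage "extrapolated exceeds 20".

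Cohort 1 receives five weekly doses, so Day 28 is dose 5. Its PK samples are taken before dosing and up to 48 h after infusion on Days 0 and 28; "Additional samples will be collected on Days 5 and 33", which is 120 h after those infusions. Cohort 2 is sampled before dosing and at 5 minutes, 1 h and 2 h after infusion on Days 0, 7, 14, 28 and 84, with Day 21 in place of Day 28 on the weekly schedule (SAP Tables 3 and 4). SAP 3.2.11 limits Cohort 2 parameters to the maximum concentration and its time.

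**The concern.** These conventions suit a single-dose profile. In such a profile, a BLQ result with measurable drug on both sides is probably an assay or sampling fault, and omitting it is sensible. Under repeat dosing, a BLQ trough has measurable drug on both sides because another dose was given. It is then a real low value, and omitting it leaves a mean over subjects who still have drug.

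Pre-dose samples are Cohort 2's only PK information on drug persisting between doses. On the every-other-week schedule, the Day 7 and 14 troughs follow a 7-day gap and the Day 28 and 84 troughs a 14-day gap. Omission is likelier after the longer gap, so it could blur the regimen and time-point contrasts that the summaries are meant to show.

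For AUC to infinity, the Day 0 figure describes one dose. The Day 28 figure also counts what remains of the previous four. Listed under one definition, a difference between them could be taken for a change in clearance.

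**Working it through.** The plan gives no figure to reproduce. It also gives no assay limit and no half-life for SYNT001, so both are treated as unknown and ranges are shown.

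**1. Which troughs the literal rule drops.** Assume that samples within 2 h of an infusion are quantifiable.

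- Cohort 2: each later pre-dose sample (Days 7, 14, 28 or 21, and 84) lies directly between the 2 h sample of the previous PK visit and the 5-minute sample of the same visit. If BLQ, it is omitted.
- Cohort 1: the Day 28 pre-dose sample lies between the Day 5 sample and the Day 28 5-minute sample. It is omitted if Day 5 is quantifiable. If Day 5 is BLQ too, there are two BLQ values in a row, and the wording does not settle what happens.

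**2. Effect on the mean trough.** With n subjects, b of them BLQ, and S the sum of the quantifiable values, omission gives S/(n−b) and the zero rule gives S/n. The ratio is n/(n−b).

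| Share BLQ (assumed) | n = 8 | n = 12 |
|---|---|---|
| one quarter | 8/6 = 1.33 | 12/9 = 1.33 |
| one half | 8/4 = 2 | 12/6 = 2 |
| three quarters | 8/2 = 4 | 12/3 = 4 |

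If all are BLQ, the table shows n = 0 and no mean, where the zero rule would show a mean of 0.

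**3. Geometric statistics.** They use the mean and SD of log concentrations, and log 0 is undefined. One zero among eight values gives a geometric mean of 0 (as the limit) and no geometric CV. This is expected at Day 0 pre-dose, where untreated subjects should be BLQ and no earlier value exists, so the zero rule applies.

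**4. Carry-over in Day 28 AUC to infinity (Cohort 1).** With linear one-phase decline and half-life h in hours, let q = 2^(−168/h). By superposition, Day 28 AUC to infinity divided by the single-dose value is R = 1 + q + q² + q³ + q⁴. The share extrapolated beyond 120 h is 2^(−120/h).

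| Half-life (assumed) | Extrapolated | R | Reported under the 20% limit? |
|---|---|---|---|
| 24 h | 3.1% | 1.008 | yes |
| 36 h | 9.9% | 1.041 | yes |
| 48 h | 17.7% | 1.097 | yes |
| 51.7 h | 20.0% | 1.117 | at the limit |
| 72 h | 31.5% | 1.247 | no |

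The limiting half-life is 120 × ln 2 / ln 5 = 51.7 h, where q = 5^(−7/5) = 0.105. A linear-up log-down calculation on the Cohort 1 sampling times gave the same ratios to within 0.002.

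**5. Beyond one phase.** For any linear profile, the carry-over is the sum of the single-dose tails beyond 168, 336, 504 and 672 h. Each is no larger than a tail already counted in the extrapolated part (beyond 120, 288, 456 and 624 h). So if at most 20% is extrapolated, and accurately, carry-over is at most 20% of the Day 28 value, and R is at most 1/0.8 = 1.25. A numerical search over two-phase profiles reached R = 1.20.

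**6. Check of the remedies, one-phase.** The pre-dose level divided by λz equals (q + q² + q³ + q⁴) times the single-dose AUC, so subtracting it recovers the single-dose value exactly. AUC over the 168 h interval at dose 5, relative to single-dose AUC to infinity, is R(1−q) = 1−q⁵. At a half-life of 84 h, q = 0.25 and the ratio is 0.999. The 0–120 h AUC on Day 28 over that on Day 0 equals R, so it measures accumulation, without extrapolation.

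**The case against.** Several points on the other side stand.

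- The BLQ rule governs mean concentrations and mean profiles only. Trough is not a named PK parameter, so a reader who infers that the secondary PK parameters are biased by this rule goes beyond the text.
- Because SAP 4.8.1 summarizes by visit and derives parameters separately for Days 0 and 28, applying the exception within one dose's profile is a plausible reading. A BLQ trough would then be set to zero. It is tempting to say flatly that mean troughs are biased upward, but the documents support this only on the literal reading. The programming specifications, which are separate documents (SAP 6), may settle it.
- With no assay limit given, nothing shows that any trough will be BLQ. Zero is itself too low, since the true value lies between zero and the limit. The ratios compare two conventions and do not measure error against the truth. The count n is reported at each time point and all data are listed, so omissions can be traced.
- A 25% inflation of AUC to infinity at a 72 h half-life might be inferred from superposition alone. The SAP would not report that value, because 31.5% would be extrapolated.
- The AUC issue concerns Cohort 1 only, up to 8 subjects. Clearance is not a planned parameter, and no Day 0 to Day 28 comparison is specified.
- The two problems do not add up in one Cohort 1 subject: a BLQ Day 28 trough means little carry-over.

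What remains is a rule that permits two different tables from the same data, geometric statistics with no rule for zeros, and one definition covering two different quantities.

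**Conclusion.** The point holds as a specification problem in descriptive PK summaries. On the literal reading, mean troughs are n/(n−b) times what the SAP's own zero rule would give. The size cannot be fixed from the documents, because b depends on an assay limit that they do not state.

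Day 28 AUC to infinity in Cohort 1 is not a single-dose quantity. Under linear one-phase kinetics, a reported value exceeds the single-dose value by 1% to 10% at half-lives of 24 to 48 h and by at most about 12%. Two-phase decline could take this to about 20%, and 25% is the ceiling for any linear profile with accurate extrapolation. Non-linear kinetics could change these figures.

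No hypothesis test, primary safety analysis or sample size depends on these summaries, and SAP 7 plans no statistical analysis for dose-escalation decisions. The changes are worth making before database lock because they are cheap and prevent misreading.

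**What to change.** In SAP 4.8.1:

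- Apply the omission only to a BLQ value within the post-dose profile of one dose. Set every pre-dose BLQ to zero, and show the number BLQ at each time point.
- Report the geometric mean and geometric CV as not calculable wherever a zero enters. A second substitute, such as half the assay limit, is not advisable: with all values BLQ, the table would show an arithmetic mean of 0 beside a larger geometric mean, which is impossible for one data set.
- Keep AUC to infinity for Day 0 as the single-dose measure. For Day 28, report AUC over the same observed 0–120 h window on both days, as a measure of accumulation. The 120 h sample may vary by ±4 h, so state how the window is brought to a common end. Alternatively, report AUC over the dosing interval, which needs extrapolation from 120 to 168 h.
- If Day 28 AUC to infinity is kept, label it as including carry-over, or subtract the pre-dose concentration divided by λz and note that this is exact only for a one-phase linear decline.

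Align Protocol 11.4, or identify the difference as SAP 1 provides for substantial ones.

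The cost is SAP wording and one added AUC derivation from planned samples. Some mean troughs become lower, and some geometric means are not reported.
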